13.7.2.1 Minor Hemorrhagic Events (Minor Bleeds) (%)

A minor hemorrhagic event (minor bleed) is defined as clinical bleeds that do not fulfill the criteria for major bleeds. Descriptive statistics and type of minor hemorrhagic event will be summarized and listed by randomization groups.

13.7.2.2 Hospitalization with any thromboembolic or major hemorrhagic event (%)

Descriptive statistics and type of event will be summarized by randomization groups.

13.7.2.3 All Cause Mortality (%)

Descriptive statistics of subjects who die during the 12-month Evaluation Period will be summarized by randomization groups. Causes of death will be listed and summarized by randomization groups.

13.7.2.4 AF Recurrence

Descriptive statistics of subjects experiencing the recurrence of AF during the 12 month Evaluation Period will be summarized by randomization group.

13.7.2.5 Repeat Ablation for AF

Descriptive statistics of subjects undergoing repeat ablations for AF during the 12-month Evaluation Period will be summarized by randomization groups.

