9.6 Subject Disposition

Evaluable Subjects

- **Enrolled Subjects:** subjects who sign the study's informed consent form
- **Randomized Subjects:** subject who remain free from arrhythmia recurrence after signing the study ICF and are randomized into one of the study arms (OAT withdrawal or OAT).
- **Completed Subjects:** enrolled subjects who have not been discontinued, withdrawn or lost-to-follow-up from the study prior to the final (12 month) study visit.
- **Lost to Follow-up Subjects:** subjects who are enrolled and randomized, but contact is lost after most recent follow-up visit (despite 3 documented attempts to contact the subject, two (2) by documented telephone calls, and one (1) written attempt sent by registered mail).
- **Discontinued:** Subjects that have arrhythmia recurrence at any time during the Evaluation Period will be discontinued. Discontinued subjects are exited from the study prior to completion of all follow-up visits; however, they will remain in the analysis cohort until the time at which they are discontinued from the study.
- **Withdrawn Subjects:** Subjects may be withdrawn for reasons stated below in Section 9.7. Withdrawn subjects are exited from the study prior to completion of all follow-up visits; however, they will remain in the analysis cohort until the time at which they are withdrawn.

Non-Evaluable Subjects

- **Excluded:** Subjects found to not meet one of the study inclusion/exclusion criteria after the being enrolled.

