10.2 Secondary Endpoints

The secondary endpoints supporting the study objective are:

Safety Endpoints:

- Minor bleeds
- Hospitalization with any thromboembolic or major hemorrhagic event
- All cause mortality

Additional Endpoints:

- QoL (SF-36)
- AF recurrence
- Repeat ablation for AF

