11.4.3 Unscheduled Visits

If a subject returns for visit outside of the protocol-defined visit windows provided in the Study Visits Section (11.4.1) of this protocol, the visit will be considered "unscheduled". If the unscheduled visit is for any purpose other than a repeat ablation procedure, an unscheduled visit CRF must be completed and the subject must also return for their next scheduled study visit. A list of the requested/recommended assessments that should be performed during the unscheduled visits is included in Table 3.0. If the unscheduled visit is for arrhythmia recurrence, the subject must be discontinued from the study as previously indicated in the Subject Disposition Section (9.6) of this protocol. All appropriate forms (eg, Final Status Form) must be completed for subjects that are discontinued due to arrhythmia recurrence within the Evaluation Period.

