13.7.2 Analysis of Secondary Endpoints

Descriptive statistics including frequency and percentage for categorical secondary endpoints will be presented. The categorical secondary endpoints include minor hemorrhagic events (minor bleeds), hospitalization with any thromboembolic or major hemorrhagic event, all cause mortality, AF recurrence and repeat ablation procedures for AF.

The 95% confidence intervals for binary outcome will be computed using exact binomial method. Descriptive statistics and 95% confidence intervals will be presented overall and by randomization groups. The proportion of the occurrence will be compared between randomization groups using the Fisher exact test.

Descriptive statistics for continuous endpoints will include number of subjects, mean, standard deviation, median, 25th and 75th percentiles, minimum and maximum. These continuous secondary endpoints include the index scores of the SF-36. Change from baseline for the index score of the SF-36 will be compared between two randomization groups using the Wilcoxon rank sum test.

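### Repeat ablation for AF is compared between arms over 12 months, but subjects leave the study at the AF recurrence that ordinarily precedes it, so the proportion is biased downward by an unknown amount

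*Combined protocol and SAP*

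**What the plan says.** Section 10.2 lists "Repeat ablation for AF" among the additional secondary endpoints. Section 13.7.2 includes it among the categorical endpoints ("all cause mortality, AF recurrence and repeat ablation procedures for AF"), gives these exact binomial 95% intervals, and states: "The proportion of the occurrence will be compared between randomization groups using the Fisher exact test". Section 13.7.2.5 sets the counting window: "Descriptive statistics of subjects undergoing repeat ablations for AF during the 12-month Evaluation Period will be summarized by randomization groups".

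The disposition rules stop observation sooner. Section 9.6: "Subjects that have arrhythmia recurrence at any time during the Evaluation Period will be discontinued". It adds: "Discontinued subjects are exited from the study prior to completion of all follow-up visits", and of the same subjects, "they will remain in the analysis cohort until the time at which they are discontinued from the study". Section 8.3 likewise ends follow-up at 12 months or at AF recurrence. Section 11.3 discontinues subjects for AF recurrence and/or a repeat ablation, and test-arm subjects also for resuming OAT. Section 11.4.3 requires discontinuation, with a Final Status Form, when an unscheduled visit is for recurrence. It also says: "If the unscheduled visit is for any purpose other than a repeat ablation procedure, an unscheduled visit CRF must be completed".

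Section 13.4 keeps discontinued subjects in the intention-to-treat analysis.

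**The concern.** A repeat ablation for AF ordinarily follows a documented recurrence. Recurrence is also the event that removes the subject from the study. The endpoint therefore sits largely behind its own exit rule: a site that follows the protocol exits the subject when the recurrence is found, and a procedure scheduled for later falls outside data collection.

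A simple proportion cannot use the provision that discontinued subjects count only until exit. If all randomized subjects form the denominator, someone exited at month 2 and re-ablated at month 5 is scored as having had no repeat ablation. The result would carry a 12-month label without being a 12-month proportion, and the Fisher test would compare two under-counts. If the under-count differs by arm, the comparison could hide a difference or create one.

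**Working it through.** **Step 1. Is there any route to the data after exit?**
- Follow-up visits: none after discontinuation (8.3, 9.6).
- Unscheduled-visit CRF: not required for a repeat-ablation visit (11.4.3).
- Procedure reports: the site keeps them for procedures done while the subject is enrolled (15.4).
- Adverse events: collected from consent to the end of the study (12.5). AF recurrence alone is generally not an AE, and a planned admission for a pre-existing condition is not an SAE (12.1).
- Final Status Form: required at a recurrence exit (11.4.3). Its fields are not described, and it would normally be completed before a later ablation.

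Nothing provides for ablation status after exit. An ablation that is itself the exit event can be recorded, because 11.3 names it as a separate trigger.

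**Step 2. Inputs.** The documents give 50 subjects per arm (13.3). They give no recurrence rate, repeat-ablation rate, alpha or power for this endpoint, so there is no plan figure to reproduce. Assumptions:
- r, AF recurrence within 12 months: 10% to 40%
- q, repeat ablation within 12 months given recurrence: 20% to 60%
- c, share of those ablations recorded at or before exit: 0 to 1
- two-sided 0.05
- denominator: all 50 randomized per arm (13.4; 13.7.2 names no other)

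**Step 3. Recorded proportion = r × q × c.** The true proportion r × q runs from 0.10 × 0.20 = 2% to 0.40 × 0.60 = 24%.

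| c | Recorded proportion | Expected count of 50 |
|---|---|---|
| 1 | 2% to 24% | 1 to 12 |
| 0.5 | 1% to 12% | 0.5 to 6 |
| 0.25 | 0.5% to 6% | 0.25 to 3 |
| 0.1 | 0.2% to 2.4% | 0.1 to 1.2 |
| 0 | 0% | 0 |

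At c = 0 each arm shows 0/50, with exact 95% upper limit 1 − 0.025^(1/50) = 7.1%. That interval misses true rates above 7.1% and covers those below it.

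**Step 4. Fisher exact power, by full enumeration with 50 per arm.**

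| True rates | c = 1 | c = 0.5 | c = 0.25 | c = 0.1 |
|---|---|---|---|---|
| 10% vs 25% | 41% | 14% | 3% | 0.1% |
| 5% vs 15% | 24% | 6% | 0.6% | 0.01% |

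Against 0/50 in one arm, the other needs at least 6/50 for p ≤ 0.05.

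**Step 5. Can capture differ between arms?** Resuming OAT ends participation in the test arm only (11.2.1, 11.3). Section 11.4.2 strongly recommends continuous rhythm monitoring for the off-OAT group and names no such recommendation for controls. Both can change when a subject exits relative to an ablation. As an illustration, take a true 20% in both arms with c = 0.1 in one and 0.5 in the other. The expected recorded rates are 0.20 × 0.1 = 2% and 0.20 × 0.5 = 10%, and the Fisher test would be significant about 19% of the time.

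**The case against.** A reader might infer that the recorded proportion will be near zero in both arms whatever the truth. The documents do not support that. Section 11.3 makes repeat ablation an exit trigger in its own right, and section 11.4.3 contemplates a subject attending for one, so some ablations can be recorded. Near zero follows only if the recorded share is near zero, and no figure for that share is given.

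Nor does the CRF exemption show that ablations go unrecorded. It waives one form, together with the duty to return for the next visit, which fits a subject who is leaving the study. Section 14.7.1 says the eCRFs will be built to capture the information in the protocol. This stands, but it reaches only procedures at or before exit.

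A third tempting inference is that a 0% rate would pass for durable ablation success. AF recurrence is reported alongside as its own endpoint (13.7.2.4), and the exit rule does not hide first recurrences, so that misreading is unlikely. The documents also state no secondary objective that the trial would fail to meet; the objective concerns the safety of stopping OAT.

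No repeat-ablation rate can be taken from the roughly 75% ablation success in section 5.1. This trial randomizes patients already free of recurrence, 3 to 21 months after ablation (9.1).

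Finally, section 13.3 says the pilot is not powered for inference, and even complete capture gives only 24% to 41% power in the scenarios above. That limits what is lost from the test. It does not excuse a proportion whose label does not match what is observed.

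**Conclusion.** The point holds in a limited form. Followed as written, the plan understates the 12-month repeat-ablation proportion, because it stops observing at recurrence, specifies no later collection and keeps the exited subjects in the denominator. The Fisher comparison cannot be read as a comparison of 12-month rates.

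The direction of the bias within each arm rests on the text and on repeat ablation ordinarily following a documented recurrence. Its size does not: it could be modest if most ablations coincide with exit, or take the figure to near zero if few do. Unequal loss between arms is possible, but neither its presence nor its direction is established. All rates in the working are assumptions. This affects one secondary endpoint and merits a short amendment.

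**What to change.** Amend 10.2, 13.7.2 and 13.7.2.5 in one of two ways.

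(a) Define the endpoint as repeat ablation performed by 12 months after randomization. Collect its date through one chart or telephone check at the month-12 date for every subject who exits early, for any reason, in either arm. Add an eCRF field and matching consent wording. The check should not be limited to recurrence exits, because resuming OAT is an exit trigger in the test arm only. The endpoint should count procedures performed; counting those merely planned would bring in an unblinded clinical intention.

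(b) Redefine the endpoint as repeat ablation at or before study exit, report it descriptively by arm, drop the Fisher test, and state that later ablations are not observed.

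Under either option, reconcile sections 8.3, 9.6, 11.3, 11.4.3, 13.7.2 and 13.7.2.5 so that the counting window, the exit rule and the form requirements agree. Neither option requires a change to treatment or to the exit rule.

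Option (a) costs a small follow-up burden, one data field and consent wording, and the comparison stays low-powered. Option (b) costs that one comparison.

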13.7.2.6 Quality of Life

SF-36

Quality of life (SF-36®) at 3 and 12months after randomization will be compared to baseline. Change from baseline in physical component summary (PCS) and mental component summary (MCS) will be calculated and tested.

13.7.3 Interim Analyses

There are no interim analyses planned for this study.

14.0 Administrative Responsibilities

14.1 Ethics Committee/Institutional Review Board (EC/IRB) Review

Before initiating this study, the Sponsor will work with the investigator to obtain approval from the EC/IRB (or equivalent) and fulfill any local, applicable requirements for notification to competent authorities. The investigator will obtain written and dated approval from the responsible EC/IRB (or equivalent) for the study protocol (or amendment[s]) and informed consent before enrollment of subjects. Biosense Webster and the EC/IRB (or equivalent) must approve in writing any changes to the protocol that affect the rights safety and/or welfare of the subjects, or may adversely affect the validity of the study.

A signed copy of the EC/IRB (or equivalent) Approval Form and a signed copy of the EC/IRB (or equivalent) approval letter addressed to the investigator must be submitted to Biosense Webster certifying study approval prior to subject enrollment. Investigators are responsible for submitting and obtaining initial and continuing review (per local regulations) of the study by their EC/IRB (or equivalent).

14.2 Informed Consent

The investigator will obtain written and dated approval from the responsible EC/IRB (or equivalent) for the study informed consent form (ICF template is provided in a separate document). A patient's informed consent must be obtained and documented per institutional, EC/IRB (or equivalent), and applicable regulatory requirements. The informed consent may be translated as appropriate.

Prior to obtaining informed consent, information should be given in a language and at a level of complexity understandable to the patient in both oral and written form by the investigator or designee. Patients should not be coerced, persuaded, or unduly influenced to participate or continue to participate in the study. A patient or his/her legal representative must be given ample time and opportunity to inquire about details of the study and all questions about the study should be answered to the satisfaction of the patient or their representative.

Prior to participation in the study, the investigator or designated member of the research team will obtain written informed consent from the subject. The background of the proposed study and the potential benefits and risks of the study should be explained to the subject. The subject or legal representative must sign the ICF prior to any study-specific exams or tests are provided to them that fall outside of the standard of care. The written ICF should be signed and personally dated by the patient or his/her legal representative, and by the person who conducted the informed consent discussion (investigator or designee) and this process should also be documented in the subjects' medical records. If the patient or his/her legal representative is unable to read the consent form, a witness should be present during the entire informed consent discussion. After the informed consent form is read to or by the patient and signed by the patient or his/her legal representative, the witness should also sign the consent form, attesting that informed consent was freely given by the patient or his/her legal representative.

The patient or his/her legal representative must receive a copy of the signed and dated informed consent form. An original copy of the EC/IRB-approved ICF must be maintained by each investigator in a designated study administrative file and a copy should be filed in the subjects medical records.

14.3 Subject Confidentiality

All information and data sent to Biosense Webster concerning subjects or their participation in this study will be considered confidential. During this study, all representatives of the Sponsor will comply with all in-country privacy laws and regulations regarding contact with subjects, their medical record information, copying of information, and protection of the subject identities. Information and data collected and used in the analysis and reporting of this evaluation will be without identifiable reference to the subject. No information that can be used to identify subjects will be collected. Only authorized Biosense Webster personnel or representative, local government authorities, or federal agencies (eg, U.S. FDA) acting in their official capacities will have access to these confidential files.

14.4 Study Monitoring

The clinical site will be monitored periodically by Sponsor personnel or an appropriately qualified and trained designee for protocol adherence, accuracy of eCRFs, verification with source documents and compliance with applicable regulations. If data entry or source documentation errors are discovered during the site visit, corrections will be made at that time by the site personnel. The monitor will create electronic data clarification queries to request data clarification or data correction, if at the time of the site visit, corrections cannot be made. The Principal Investigator will sign off for the accuracy of the final data reported to the Sponsor.

Each monitoring visit may include, but is not limited to, the following:

- Verification that the informed consent was properly obtained for all subjects and completed prior to any study required test(s)
- Confirm that randomization procedures are being followed
- Source document verification against the eCRFs
- Verification of a complete Regulatory Binder; Delegation of Responsibility Log, etc.
- Identification and management of any issues or problems with the study

Biosense Webster may request further documentation such as investigator and/or electrophysiology (EP lab procedure notes when complications or product malfunctions are observed. To this end, the investigator and institution must permit inspection of the study files and subjects' eCRFs by Sponsor personnel.

14.5 Management of Protocol Amendments

All instructions described in this study protocol are to be followed. If an amendment is required, it must be made in written form and receive approval from persons (or their designee if they are no longer available to review and approve the protocol) and authorities who approved the original protocol. Administrative changes (which do not affect patient's benefits/risks ratio) may be inserted with abbreviated approval. All amendments will be distributed to all original protocol recipients.

14.6 Management of Protocol Deviations

The investigator will not deviate from the protocol without **prior notification to and written approval** from Biosense Webster, Inc. except or in unforeseen, isolated instances to protect the safety and well being of the subject. In medical emergencies, prior approval for protocol deviations will not be required, but the Biosense Webster clinical operations personnel must be notified within 5 days of the deviation. All protocol deviations will be documented and followed up according to the applicable Standard Operating Procedures (SOPs). Any evident pattern of non-compliance with respect to applicable standards will be cause for the site to be put on probation. If corrective actions are not subsequently undertaken, the site will be asked to withdraw.

14.7 Data Management

The Sponsor or designee will perform all data management activities for this trial. These activities include development and validation of a clinical database, into which all study data will be entered. The Sponsor or designee will be responsible for ensuring overall integrity of the data and database.

14.7.1 Data Collection

Electronic Case Report Forms (eCRFs) will be used to collect all subject data during this trial. The eCRFs will be developed to capture the information outlined in this protocol. Data collected on these eCRFs will be analyzed as defined in the study protocol. Modification of the eCRFs will only be made if deemed necessary by Biosense Webster.

14.7.2 Data Reporting

The investigator, or a designated individual, is responsible for ensuring that study data are properly recorded on each subject's eCRFs and related documents.. The investigator is required to electronically sign the eCRF on the appropriate pages to verify that he/she has reviewed and attests to the correctness of the recorded data. Completed eCRFs will be monitored by Biosense Webster personnel, or an appropriately qualified and trained designee, at regular intervals throughout the trial. The investigator and institution must permit the inspection of any trial-related documentation and eCRFs by such representatives and/or responsible government agencies.

All eCRFs should be completed by the designated site personnel within 14 days of the subject visit. For AE reporting, refer to the Adverse Event Reporting Requirements and timelines within this study protocol.

14.7.3 Source Documentation

Source documents will serve as the basis for monitoring the eCRFs. Source documents may include subject's medical records, hospital charts, clinical charts, the investigator's subject study files, admissions and discharge summaries, as well as the results of diagnostic tests such as X-rays, laboratory tests, and electrocardiograms.

If no standard hospital or office document exists to capture information that may be unique to this study, a worksheet may be developed to record this information, which shall be signed by the PI at the given site and serve as the source document for unique study data.

Electronic subject records will be considered source documents on the condition that the hospital's database is a validated system. If this is not the case, electronic records will have to be printed and added to the subject's paper file. A print-out of an eCRFs cannot be used as source documentation.

Regulations require that investigators maintain information in the subject's medical records, which corroborate data collected on the eCRFs. In order to comply with these regulatory requirements, at minimum, the following is a list of information that should be maintained on source documentation:

- Medical history/physical condition of the study subject before involvement in the study sufficient to verify protocol selection criteria (if not already present).
- Dated and signed notes on the day of entry into the study including the name of the study sponsor (Biosense Webster), protocol number, clinical site identifier, subject number assigned and a statement that consent was obtained.
- Dated and signed notes from each study visit with reference to the eCRFs for further information, if appropriate (for specific results of procedures and exams).
- AEs reported and their resolution, including supporting documents such as discharge summaries, EP lab reports, ECGs, lab results, etc.
- Notes regarding protocol-required medication and prescription medications taken during the study (including start and stop dates).

- Study subject's condition upon completion of or withdrawal from the study.

